7.5 Endpoint Definitions

Clinical remission: SF subscore = 0 or 1, RB subscore = 0, and $ES \leq 1$ (excluding friability)

Clinical response using MMS: $A \geq 2$ -point and $\geq 30\%$ decrease from baseline in MMS, and a ≥ 1 -point decrease from baseline in RB subscore or an absolute RB subscore ≤ 1

Clinical remission using total MCS: Total MCS ≤ 2 points with no individual subscore > 1 point (SF subscore = 0 or 1, RB subscore = 0, $ES \leq 1$ [excluding friability], Physician Global Assessment [PGA] ≤ 1 , and SF + RB + ES + PGA ≤ 2)

Clinical response using total MCS: $A \geq 3$ -point and $\geq 30\%$ decrease from baseline in total MCS, and a ≥ 1 -point decrease from baseline in RB subscore or an absolute $RB \leq 1$.

Endoscopic improvement: $ES \leq 1$ (excluding friability)

Endoscopic remission: $ES = 0$

Histologic improvement

- Primary: Geboes Index score < 3.1
- Sensitivity: Robarts Histopathology Index (RHI) $\geq 50\%$ reduction from baseline or $RHI \leq 3$
- Sensitivity: Nancy Histopathology Index (NHI) ≥ 1 point reduction from baseline

Histologic remission

- Primary: Geboes Index score < 2.0
- Sensitivity: $RHI \leq 3$ with scores of 0 for both Geboes Grade 2B and Grade 3
- Sensitivity: $NHI \leq 1$

Endoscopic improvement-histologic remission: $ES \leq 1$ (excluding friability) and histologic remission measured by a Geboes Index score < 2.0

Endoscopic remission with histologic remission: $ES = 0$ and histologic remission measured by a Geboes Index score < 2.0

Histologic-endoscopic mucosal improvement (HEMI): $ES \leq 1$ (excluding friability) and histologic remission measured by a Geboes Index score < 3.1

Symptomatic remission

- Primary: SF subscore = 0 or 1 and RB subscore = 0
- Sensitivity: SF subscore = 0 (or =1 with a ≥ 1 -point decrease from baseline) and RB subscore = 0

Symptomatic response: Decrease from baseline $\geq 30\%$ of the combined RB and SF subscores

Endoscopic and clinical remission: SF subscore ≤ 1 , RB subscore = 0, and ES subscore = 0

Endoscopic remission with histologic remission and clinical remission: SF subscore ≤ 1 , RB subscore = 0, ES subscore = 0, and histologic remission measured by a Geboes Index score < 2.0

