8. ANALYSIS SETS

The following analysis sets for the Induction Treatment Period are defined as follows:

Full Analysis Set (FAS): The FAS consists of all randomized participants receiving at least 1 dose of study treatment. Under this approach, participants are counted in the treatment group to which they were randomized, regardless of the treatment received during the study.

Modified Full Analysis Set (mFAS): For a given endpoint (see [Section 23](#), Appendix II), mFAS consists of all randomized participants who received at least 1 dose of study treatment and contribute at least one complete endpoint assessment for at least one post-baseline Induction visit. Participants will be analyzed according to the treatment to which they were randomized.

Per Protocol (PP) Set: The PP Set consists of all participants in the primary endpoint mFAS who received $\geq 80\%$ and $\leq 120\%$ of study treatment and do not have a protocol deviation preventing contribution to the primary analysis of the primary efficacy endpoint. Participants experiencing an intercurrent event during the Induction Treatment Period and not experiencing other deviations preventing contribution to the primary and key secondary analyses of the primary and key secondary efficacy endpoints will be included in the PP set and treated as non-responders in these analyses ([Section 3.5](#)).

Safety Set: The Safety Set consists of all randomized participants who received at least 1 dose of study treatment. For this population, participants are analyzed according to the treatment received, regardless of randomization. The Safety Set will be used for all safety analyses in the Induction Treatment Period.

The following analysis sets for the LTE and OLE Treatment Periods are subsets of the analysis sets of the Induction Treatment Period, as defined below:

FAS-Extension Treatment (FAS-ET) Set: The FAS-ET Set consists of all randomized participants who received at least 1 dose of study treatment in the LTE or the OLE Treatment Period. Under this approach, the original treatment groups as assigned at randomization will be used throughout LTE. In general, participants will be analyzed according to protocol-specified intended study treatment dose in FAS-ET analyses. Additional details are provided for specific analyses described elsewhere in this SAP.

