data from ET and Unscheduled visits not associated with Visit 7 will be listed only. 1-Week and 2-Week Follow-up data is not windowed and presented according to nominal visit label in tables.

For composite scores such as MMS, if one or more components is missing from an analysis visit window the composite score is missing. If one or more results for a variable are assigned to the same analysis visit, the result with the date closest to the protocol Ideal Study Day will be used in the analysis, except for rectal bleeding and stool frequency component subscores used in the determination of Symptomatic Remission, Symptomatic Response, MMS, or total MCS. In this case, 7-day look-back windows anchored to either an endoscopy or a site visit are used to determine the component subscores.

If two measurements in the same analysis visit window are equidistant from the protocol scheduled study day, the earliest measurement will be used in the analysis. If multiple assessments are available on the same day, then the average of the assessment will be used in the analysis, except for laboratory data where the assessment at the earliest time of the same day will be used. Central laboratory assessments will be used in both summaries and listings, while local laboratory assessments will only be separately listed. Local laboratory data may be used by investigators to help inform participant safety decisions and adverse event reporting.

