16.1.2 Missing Data Methods for the Primary Efficacy Variable

The concept of non-response for participants with non-missing Week 13 Induction primary efficacy outcomes is described at the beginning of [Section 16](#). For participants with missing Week 13 Induction Treatment Period primary efficacy outcomes, the following missing data methods will be used:

- Primary method: single imputation as non-responder
- Sensitivity analyses
 - multiple imputation under missing at random (MAR)
 - multiple imputation with Copy Reference (CR) under missing not at random (MNAR)
 - tipping point analysis
- Supplementary analyses: mFAS and PP set analysis with data as observed

These methods are discussed in more detail below. See [Section 29](#) (Appendix VIII) for a tabular presentation of the relationship between intercurrent events, missing data, and response imputation.

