16.1.4.3 Tipping Point Analysis

A tipping point approach based on multiple imputation of Visit 7 Week 13 responses with respect to the primary endpoint will be used². This will be an MNAR-based imputation approach in

² <https://www.pharmasug.org/proceedings/2023/SD/PharmaSUG-2023-SD-069.pdf>

which direct Bernoulli simulation is used to evaluate the robustness of the obtained primary efficacy results with respect to various assumed response rates in each treatment arm.

The following steps will be implemented:

Step 1:

Participants not contributing observed RB, SF, and ES at Visit 7 Week 13 will be assumed to have primary efficacy response rates that vary according to the following thirty-element lists:

VTX002 60 mg: $p_{VTX} \in \{0\%, 2\%, 4\%, \dots, 30\%, 35\%, 40\%, \dots, 95\%, 100\%\}$

Placebo: $p_{PBO} \in \{0\%, 2\%, 4\%, \dots, 30\%, 35\%, 40\%, \dots, 95\%, 100\%\}$

Step 2:

- a. Consider all possible combinations of primary efficacy response rates. This yields 900 pairs of response rates.
- b. Fix attention to a specific pair of response rates. An example of such a pair would be ($p_{VTX} = 14\%$, $p_{PBO} = 35\%$).
 - i. Imputation #1: Assign responder or non-responder status to each participant not contributing observed RB, SF, and ES at Visit 7 Week 13. This will be done, per participant, by drawing $N=1$ random draws from a Binomial distribution having an appropriate probability from the response rate pair. An example of such a random draw would be generating $X_i \sim \text{Bin}(n=1, p_{PBO} = 35\%)$ for each i , where i indexes all placebo participants not contributing observed RB, SF, and ES at Visit 7 Week 13.
 - ii. Repeat until 40 total imputations have been generated
- c. Repeat 2b until all possible pairs of response rates have been handled.

Step 3:

Same as Step 3 described in [Section 16.1.4.1](#).

Step 4:

Same as Step 4 described in [Section 16.1.4.1](#).

Results will be plotted as a heat map on a two-dimensional plot with axes corresponding to the assumed primary efficacy response rates applied to each treatment group respectively, and different colors will be used to represent the magnitude of the 2-sided p -values corresponding to analysis with each combination of delta values. The clinical interpretation about the plausibility of the assumptions underlying the tipping point will be provided in the CSR.

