16.2 Key Secondary Analyses

Key secondary efficacy endpoints are defined in [Section 7.2](#):

- Hypothesis testing of these endpoints for VTX002 60 mg versus placebo are considered key secondary analyses
- Hypothesis testing of the primary efficacy endpoint for VTX002 30 mg versus placebo, in addition to hypothesis testing of the key secondary efficacy endpoints for VTX002 30 mg versus placebo, are also considered key secondary analyses

The primary analyses of these hypothesis tests are subject to the family-wise Type 1 error rate handling and gatekeeping (i.e., multiplicity adjustments) described in [Section 10.3](#). After attribution of known outcome at Induction Week 13 (see introduction to [Section 16](#)), the primary planned Key Secondary Analyses as described [Table 6](#) will be conducted.

The CMH methodology used for the primary analysis of the primary endpoint will be used for all Key Secondary Analyses. The additional primary endpoint analysis methods described in [Sections 16.1.4](#) and [16.1.6](#) – missing data methods (MAR multiple imputation, copy reference multiple imputation, tipping point), randomization stratification factor (EDC) sensitivity analysis, and supplementary analyses (application of mFAS and PP analysis sets to primary analysis methods) – will also be applied to the Key Secondary endpoints. See [Table 6](#).

For tipping point analyses, identification of participants not contributing observed data at Visit 7 Week 13 will rely on the types of data needed for a given Key Secondary endpoint. For example, endoscopic improvement-histologic remission (the fourth Key Secondary endpoint) requires Geboes and ES to both be available. If they are not available for a given participant, that participant will be subject to tipping point analysis. The set of participants subject to tipping point analysis may differ from one endpoint to another.

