23. APPENDIX II. RELATIONSHIP OF MFAS TO ENDPOINTS

Table 9. Relationship of Primary Endpoint and Key Secondary Endpoints to Post-Baseline Assessments Occurring at the Same Visit

	Primary Endpoint	Key Secondary Endpoints			
Non-Missing Assessments at the Same Post-Baseline Visit	Clinical Remission	Endoscopic Improvement	Symptomatic Remission	Histologic Remission	Endoscopic improvement-histologic remission
ES		☑			
Geboes				☑	
ES, Geboes					☑
RB, SF			☑		
ES, RB, SF	☑				

For example, in order for a participant to contribute non-trivially to Symptomatic Remission at Induction Treatment Period Week 13 (Visit 7), their RB and SF scores must both be available at the Week 13 visit, according to the Visit Windows described in [Section 9.6](#). Because such a participant contributes *at least one* complete post-baseline Induction Treatment Period set of assessments for Symptomatic Remission, they are members of mFAS at *all* Induction Treatment Period post-baseline visits for Symptomatic Remission. This is true even if (say) Symptomatic Remission cannot be determined at Week 8 (Day 57) because SF is missing at Week 8.

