28. APPENDIX VII. DETERMINATION OF SAMPLE SIZE

Based on literature data review, the expected proportion of clinical remission at Induction Week 13 is 28% for VTX002 60 mg and 8% for placebo (Sandborn 2016; Sandborn 2020). Under these assumptions, and with a 1:1 randomization ratio, 2-group chi-squared test, and two-sided significance level of 5%, a sample of 57 participants per treatment group will be sufficient to achieve at least 80% power. Adding a 10% inflation for dropouts results in 63 participants per treatment group and 189 participants in total.

Software

SAS (version 9.4; SAS Institute Inc.; Cary, NC, USA).

Input & Output

Fixed Scenario Elements	
Distribution	Asymptotic normal
Method	Normal approximation
Number of Sides	2
Alpha	0.05
Group 1 Proportion	0.08
Group 2 Proportion	0.28
Nominal Power	0.8
Null Proportion Difference	0

Computed N per Group	
Actual Power	N per Group
0.802	57

29. APPENDIX VIII. RELATIONSHIP OF INTERCURRENT EVENTS TO NON-RESPONDER IMPUTATION, MULTIPLE IMPUTATION, COPY REFERENCE IMPUTATION, AND TIPPING POINT

Table 12. Relationships Between Various Types of Imputation and Data Missingness

Type of Occurrence	Visits Affected	Effect of Protocol Deviations	Primary Analysis of Primary, Key Secondary, and Other Secondary Endpoints	Multiple Imputation	Copy Reference	Tipping Point
Intercurrent Event	All visits on/after intercurrent event, regardless of data missingness for other reasons . Intercurrent event handling takes priority over missing data handling.	An intercurrent event is a major protocol deviation. As long as other deviations don't prevent the participant from being Per Protocol, they will be included in the PP Set.	Non-responder imputation	Non-responder imputation	Non-responder imputation	Non-responder imputation
Missing Data	Visits w/ efficacy endpoints having missing values in one or more endpoint components.	As long as there are no intercurrent events, missing data is handled per this row in the table.	Non-responder imputation	Multiple imputation	Copy reference imputation	Tipping point imputation

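### The tipping-point draws and the mFAS/PP rules treat participants with partial Week 13 data as unknown even when an observed component already rules out response

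*SAP*

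**What the plan says.** The primary endpoint is a conjunction. SAP 7.5 gives "Clinical remission: SF subscore = 0 or 1, RB subscore = 0, and" an ES of at most 1. Endoscopic improvement-histologic remission is also a conjunction (ES and Geboes).

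- **Composite scores (9.6, repeated in Section 16).** "For composite scores such as MMS, if one or more components is missing from an analysis visit window the composite score is missing".
- **Tipping point, primary endpoint (16.1.4.3).** "Participants not contributing observed RB, SF, and ES at Visit 7 Week 13 will be assumed to have primary efficacy response rates" running from 0% to 100% in each arm. Responder status itself is drawn as a Bernoulli variable.
- **Tipping point, key secondary endpoints (16.2).** For endoscopic improvement-histologic remission, Geboes and ES must both be present. "If they are not available for a given participant, that participant will be subject to tipping point analysis".
- **Appendix VIII, Table 12.** The missing-data row covers "Visits w/ efficacy endpoints having missing values in one or more endpoint components" and assigns tipping-point imputation in the tipping-point column. Intercurrent events are non-response in every column and take priority over missing-data handling.
- **mFAS (Section 8).** Participants must "contribute at least one complete endpoint assessment for at least one post-baseline Induction visit". Table 9, under "Non-Missing Assessments at the Same Post-Baseline Visit", requires ES, RB and SF together for clinical remission. The PP set is drawn from the primary-endpoint mFAS.
- **Use of these sets (16.1.2).** "Supplementary analyses: mFAS and PP set analysis with data as observed".
- **Diary rule (10.3).** In describing the guidance algorithm that the SAP means to match, it says that too few diary days makes the score missing and the participant a non-responder.
- **Multiple imputation (16.1.4.1, 16.1.4.2).** Missing component scores are imputed first, and response is derived afterwards.

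**The concern.** An endpoint that requires every component to pass is decided by one observed failure. It is unknown only if nothing observed fails and something is missing. The SAP has no rule that separates these two situations.

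The affected participants have partial Week 13 data and no intercurrent event. The main case is an endoscopy read as ES 2 or 3 with an unusable diary. A rarer case is a failing RB, SF or Geboes alongside an endoscopy that was performed but has no usable ES; Table 3, footnote b, anticipates endoscopies with missing ES.

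At stake is the meaning of two sets of pre-specified supporting analyses. The tipping-point heat map would include outcomes that the data exclude, yet the CSR must interpret how plausible the tipping point is. The mFAS and PP remission rates would lose only known failures, never known successes, because partial data can prove failure but cannot prove remission.

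**Working it through.** **1. The same participant through each analysis.** Take central ES = 3 at Visit 7, too few diary days for RB and SF, and no intercurrent event.

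| Analysis | Handling as written | Uses the observed ES? |
|---|---|---|
| Primary, FAS (16.1.2) | Non-responder | Result agrees |
| MAR imputation (16.1.4.1) | RB, SF imputed; ES = 3 kept; non-responder in all 40 datasets | Yes |
| Copy reference (16.1.4.2) | Components imputed; ES = 3 kept; non-responder | Yes |
| Tipping point (16.1.4.3, Table 12) | Bernoulli draw; responder with the assumed rate | No |
| mFAS and PP (Section 8, Table 9) | Excluded | No |
| Diary rule (10.3) | Non-responder, scope across analyses not stated | Result agrees |

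An earlier visit cannot restore primary mFAS membership, because Table 3, footnote d, lets post-baseline endoscopy map only to Visit 7.

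In the tipping point, one such participant at an assumed rate of 2% is drawn as a responder at least once in 40 imputations with probability 1 − 0.98^40 = 0.55. At 100% the participant is a responder in all 40.

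**2. Anchor to the plan's own figures.** For 28% vs 8%, two-sided 5%, 80% power, pooled chi-square:

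n = [1.960·√(2·0.18·0.82) + 0.842·√(0.28·0.72 + 0.08·0.92)]² / 0.20² = 56.7, so 57 per arm. Then 57 × 1.1 = 62.7, so 63. Both match SAP Section 6. These figures are not in dispute. They give round illustrative counts: 63 × 0.28 = 17.6 (18) and 63 × 0.08 = 5.0 (5).

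**3. Tipping point: assumed counts, unstratified pooled z-test.** z = (p1 − p2)/√[p(1 − p)(2/63)].

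Start from 18/63 vs 5/63: difference 20.6 points, z = 3.00, p = 0.0027. Assume 4 placebo participants have an endoscopy but no usable diary, and 3 of them have ES of 2 or 3. At the corner VTX002 0%, placebo 100%:

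- As written, all 4 become responders: 18 vs 9, z = 1.95, p = 0.051.
- Drawing only the 1 undetermined participant: 18 vs 6, z = 2.72, p = 0.0065.
- From 16 vs 5 instead (p = 0.0086): 16 vs 9, p = 0.118, against 16 vs 6, p = 0.019.

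The error runs the other way if the incomplete participants are on VTX002. With the same 4 and 3, at VTX002 100%, placebo 0%: as written 22 vs 5, difference 27.0 points; after the fix 19 vs 5, difference 22.2 points.

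**4. mFAS: assumed counts.** Take 57 complete per arm with 16 and 5 remitters. Put back 2 to 4 known failures on VTX002 60 mg and 3 to 5 on placebo.

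| | VTX002 60 mg | Placebo | Difference | p |
|---|---|---|---|---|
| As written | 16/57 = 28.1% | 5/57 = 8.8% | 19.3 points | 0.0079 |
| 2 and 3 kept | 16/59 = 27.1% | 5/60 = 8.3% | 18.8 points | 0.0072 |
| 4 and 5 kept | 16/61 = 26.2% | 5/62 = 8.1% | 18.2 points | 0.0074 |

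The difference moves by 0.5 to 1.1 points.

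**The case against.** **Section 10.3 already covers the main case.** If its non-responder rule governs every analysis, ES 2 or 3 with an unusable diary is never drawn. But 16.1.2 makes non-responder imputation the primary method only, and 16.1.4.3 and Table 12 prescribe a draw for the same participants. Nor does 10.3 address a missing ES or Geboes, or mFAS membership. What stands is that the sections conflict and must be reconciled.

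**Intercurrent events remove most cases.** A reader might infer that a response is drawn for everyone lacking RB, SF or ES. The documents do not support that. Under Section 16 and Table 12, a missed Week 13 endoscopy in an eligible participant, rescue therapy, and discontinuation for disease worsening or a UC adverse event stay non-response in the tipping point. Protocol 8.3.1.2 also allows a repeat endoscopy when the video is inadequate, so the missing-ES case is narrow. This limits the point to partial data with no intercurrent event.

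**The 9.6 sentence is sound.** It is: a sum with a missing term is missing. The fault lies in 16.1.4.3, 16.2 and Tables 9 and 12.

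**The example sits at one extreme of 900 grid points.** Also correct. Substituting expected counts for the draws, a simplification, the as-written example gives p = 0.008 at a 30% placebo rate, 0.028 at 75% and 0.045 at 95%; only 100% crosses 0.05. With 4 truly undetermined placebo participants, that corner would reach 0.051 even after the fix.

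**Conclusion.** The point holds for participants with partial Week 13 data, no intercurrent event and an observed failing component. For them the tipping-point analysis can draw a response that the data exclude, the clinical-remission mFAS and PP drop a known failure, and both conflict with 10.3 and with the MAR and copy-reference analyses.

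Three stronger readings are not supported:

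- The primary and key secondary FAS results are not affected, because missing endpoints are already non-responses there.
- The tipping-point error does not always favour the drug. Placebo failures drawn as responders make the map too harsh; VTX002 failures drawn as responders make it too favourable.
- The mFAS effect is not a material inflation of the treatment effect. Arm rates rise slightly, but in the example the as-written p-value is marginally less favourable.

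The size is unknown, because the documents give no counts of partial data. The p = 0.051 against 0.0065 contrast rests on assumed counts, an unstratified test and one extreme corner. The 0.5 to 1.1 point mFAS shift rests on assumed counts as well. The analyses concerned are supportive and tested at nominal alpha (SAP 10.4). The inconsistency is nonetheless clear on the page and cheap to remove.

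**What to change.** In SAP Sections 16, 16.1.4.3 and 16.2 and in Tables 9 and 12, state that for responder endpoints requiring all components to pass, any observed component that fails its criterion makes the participant a non-responder in every analysis. Then:

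- Limit tipping-point draws to participants with no intercurrent event, no observed failing component and at least one missing component.
- Keep known failures in the mFAS as non-responders, and likewise in the PP set if its other criteria are met.
- Reconcile 10.3 with 16.1.2 and Table 12, saying whether the insufficient-diary rule applies to the primary analysis only or to all analyses.
- Leave the 9.6 rule for summed scores such as MMS as it is.

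The cost is SAP wording and one derivation flag, with no new data. The primary result does not change. mFAS and PP remission rates would be equal or slightly lower.
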